**Part B Visits:**

For efficacy and safety by-visit analyses, data collected at the ET visit during open-label treatment will be included and assigned to the EOT visit. Data collected at unscheduled visits during open-label treatment will not be included in any analyses.

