#### **8.4. Safety Endpoints**

The following safety endpoints will be assessed in Part A:

- Incidence of adverse events, serious adverse events, severe adverse events, drug-related adverse events, adverse events leading to withdrawal during the following periods:
  - Overall
  - During titration
  - During long-term treatment
- Observed values and changes from baseline in clinical laboratory parameters (hematology, chemistry, and urinalysis)
- Observed values and changes from baseline in vital signs
- Observed values in ECG parameters and abnormal findings
- Number of subjects with on-treatment QTcF values >450 ms, >480 ms, >500 ms, or a change from Baseline in QTcF of >30 ms or >60 ms
- Observed values and changes in UPDRS Part III (motor examination), BARS, HADS, C-SSRS, ESS, and MoCA©
- Duration of time to achieve stable dosing of SD-809

The following secondary safety endpoints will be assessed in Part B:

- Incidence of adverse events, serious adverse events, severe adverse events, drug-related adverse events, and adverse events leading to withdrawal
- Observed values and changes from start of randomized withdrawal in clinical laboratory parameters (hematology, chemistry, and urinalysis)
- Observed values and changes from start of randomized withdrawal in vital signs
- Observed values in ECG parameters and abnormal findings
- Number of subjects with on-treatment QTcF values >450 ms, >480 ms, >500 ms, or a change from Baseline in QTcF of >30 ms or >60 ms
- Observed values and changes in UPDRS Part III (motor examination), BARS, HADS, C-SSRS, ESS, and MoCA©

The following secondary safety endpoints will be assessed in Part C:

- Secondary safety endpoints:
  - Incidence of adverse events, serious adverse events, severe adverse events, drug-related adverse events, and adverse events leading to withdrawal from start of Part C
  - Observed values and changes in vital signs from start of Part C
  - Observed values and changes in C-SSRS from start of Part C
  - Observed values in ECG parameters and abnormal findings from start of Part C

- Number of subjects with on-treatment QTcF values >450 ms, >480 ms, >500 ms, or a change from Baseline in QTcF of >30 ms or >60 ms from start of Part C

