##### **Part A Visits:**

For efficacy and safety by-visit analyses, data collected at post baseline scheduled visits will be included using their scheduled visit and data collected at early termination and unscheduled visits will be included and assigned to a visit window as described below. After the assignments are made use the following rules: if there is a scheduled visit with an early termination and/or unscheduled visit in the same visit window, the scheduled visit will be used in the analysis; if there is no scheduled visit but an early termination and unscheduled visit in the same visit window, the early termination visit will be used in the analysis; if there is no scheduled or early termination visit but an unscheduled visit in a visit window, the unscheduled visit will be used in the analysis.

Efficacy: Visit Windows for Early Termination and Unscheduled Visits

Visit	Study Day		
	AIMS site	CGIC, PGIC	mCDQ-24
Week 2	2 to 21		
Week 4	22 to 35	2 to 35	
Week 6	36 to 74	36 to 74	2 to 74
Week 15	75 to 151	75 to 151	75 to 151
Week 28	152 to 242	152 to 242	152 to 242
Week 41	243 to 328	243 to 328	243 to 328
Week 54	329 to 424	329 to 424	329 to 560
Week 67	425 to 515	425 to 515	
Week 80	516 to 606	516 to 606	
Week 93	607 to 697	607 to 697	
Week 106	698 to 788	698 to 788	561 to 924
Week 119	789 to 879	789 to 879	
Week 132	880 to 970	880 to 970	
Week 145	971 to 1061	971 to 1061	
Week 158	1062 to 1110	≥1062	≥925
Follow-up	≥1111		

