**Part A and B Combined:**

Some analyses, such as the analyses of adverse events, will be performed by time period. For these analyses, the following definitions will be used:

- Titration Period - from the first dose of treatment until 7 days after the week 6 visit. If a patient discontinues treatment before 7 days after the week 6 visit, then the Titration Period is until the last dose of treatment.
- Maintenance Period - from 8 days after the week 6 visit until the day of the week 158 visit for patients only in Part A and until the day of the open-label treatment EOT visit for patients in both Parts A and B. If a patient enters the Maintenance Period but discontinues treatment early, the Maintenance Period is until the last dose of treatment.

- Overall Treatment Period - includes the Titration and the Maintenance Periods, if applicable.
- Follow-up Period - from the end of the Overall Treatment Period through the end of the study.

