## **7. SAFETY ANALYSIS**

### **7.1. Part A**

#### **7.1.1. General**

The safety population will be used for all safety summaries. Summaries will be presented by parent study treatment group and overall. Summaries will be presented for Parts A and B combined unless otherwise noted.

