#### **7.1.3. Adverse Events**

All AEs will be coded using MedDRA. Summaries will be presented in the overall treatment period (titration plus maintenance treatment period) for all AEs (overall and by severity), AEs determined by the investigator to be treatment-related, serious AEs, AEs causing discontinuation from the study, non-serious AEs, AEs leading to dose reduction, and AEs leading to dose suspension. In addition, all AEs will be summarized separately for the titration period, maintenance treatment period, and follow-up period.

All AEs in the overall treatment period will be summarized by strong CYP2D6 inhibitor status (Yes/No), poor CYP2D6 metabolizer phenotype status (Yes/No), impaired CYP2D6 function

status (Yes/No), baseline use of DRA status (Yes/No), and background comorbid illness type. In addition, serious AEs and AEs by severity will be summarized by impaired CYP2D6 function status.

The incidence of adverse events will be summarized using descriptive statistics by system organ class and preferred term. Patients are counted only once in each system organ class category and only once in each preferred term category. For all AEs in the overall treatment period, the event rate will also be presented. The event rate is defined as  $100 * (\text{total number of AEs} / \text{patient years of treatment in Parts A and B combined})$ . Treatment-related adverse event summaries will include adverse events with possible, probable, definite, or missing relationship to study drug. For the summaries by severity, patients are counted at the greatest severity only once in each system organ class category and only once in each preferred term category.

The Standard MedDRA Queries (SMQs) of depression (excl suicide and self injury), suicide/self-injury, akathisia, Parkinson-like events, and Torsade de pointes/QT prolongation AEs, and somnolence and sedation AEs of interest as specified in [Appendix A](#) will be summarized using descriptive statistics. In addition, time to first SMQ AE or AE of interest will be presented using Kaplan-Meier curves for each SMQ AE or AE of interest. For this analysis, patients who do not experience the event will be censored at the end of treatment in Parts A and B combined.

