#### **7.1.7. Electrocardiogram**

Shifts (normal, abnormal not clinically significant, and abnormal clinically significant) from baseline of this study to each Part A visit that this is measured will be summarized using patient counts.

The number of patients with postbaseline QTcF values >450 ms, >480 ms, >500 ms, or a change from baseline in QTcF of >30 ms or >60 ms, PR interval values >200 ms, QRS duration values >100 ms, and QT interval values >500 ms will be summarized using descriptive statistics. This summary will be repeated for patients who have a normal QTcF at baseline according to the protocol definition.

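### SAP 4.5 bars Part B open-label unscheduled-visit data from every analysis; as written, this drops ECGs from the only outlier count that covers that phase

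*SAP*

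**What the plan says.** SAP 4.5 has three blocks on how data are placed in time.

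- **Part A Visits.** For by-visit analyses, "data collected at early termination and unscheduled visits will be included and assigned to a visit window as described below".
- **Part B Visits.** The first sentence, again for by-visit analyses, assigns open-label early-termination (ET) data to the end-of-treatment (EOT) visit. The second reads: "Data collected at unscheduled visits during open-label treatment will not be included in any analyses".
- **Part A and B Combined.** This block covers analyses by time period and names adverse events as an example. For patients who enter Part B, the Maintenance Period runs "until the day of the open-label treatment EOT visit for patients in both Parts A and B".

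The safety tables concerned are in SAP 7.1. Section 7.1.1 sets the default: "Summaries will be presented for Parts A and B combined unless otherwise noted". Section 7.1.7 then plans a count that is not tied to Part A visits: "The number of patients with postbaseline QTcF values >450 ms, >480 ms, >500 ms", together with QTcF change, PR, QRS and QT limits. Section 7.1.11 plans any-time postbaseline and shift tables for the C-SSRS. For Part B alone, SAP 7.2.6 plans only shifts between normal and abnormal ECG categories, and SAP 9 says ECG variables will not be analysed by visit.

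Protocol 8.4 opens its Part B list with "The following secondary safety endpoints will be assessed in Part B" and includes "Number of subjects with on-treatment QTcF values >450 ms, >480 ms, >500 ms". It does not confine that item to the withdrawal week.

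**The concern.** The two sentences of the Part B paragraph differ in scope. The first is about by-visit analyses; the second covers all analyses. A programmer who follows the second literally would filter out every open-label unscheduled record before building the combined any-time tables.

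Some of the ECGs concerned are ones the protocol requires. Note 11 to the Part B Schedule of Events and Protocol 6.7.1 call for additional ECG monitoring, at an unscheduled visit, when an antipsychotic is increased, switched or added. Protocol 6.11.1 permits changes in psychoactive medication after three months with the investigator's approval. These readings are collected because of QT risk, and the wording would keep them out of the table that counts QT outliers.

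What is at stake is a descriptive safety count in a long-term safety study. An omission of this kind can lower the count but never raise it.

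**Working it through.** The plan gives no figure for this point, so there is none to reproduce. The check sets the sections side by side and then sizes the exposure.

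**1. Which tables does the literal sentence reach?**

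| Planned analysis | Effect of the sentence |
|---|---|
| Primary endpoint (SAP 6.2.2) | None. It uses the Pre- and Post-Withdrawal Visits; the sentence covers only the later open-label phase. |
| Adverse events (SAP 7.1.3) | Governed by the time-period block. The section says: "Summaries will be presented in the overall treatment period (titration plus maintenance treatment period) for all AEs". The wording is inconsistent with this, but a specific rule exists. |
| Combined ECG outlier counts (SAP 7.1.7) | Open-label unscheduled ECGs removed. |
| Part B ECG shifts (SAP 7.2.6) | By visit; no outlier count. |
| C-SSRS any-time and shift tables (SAP 7.1.11) | Unscheduled responses could be removed. |

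**2. Is there another count of open-label Part B outliers?** No. SAP 7.2.6 has category shifts only, and SAP 9 drops by-visit ECG variables. SAP 7.1.7 is the only planned outlier count that covers this phase.

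**3. When does a patient disappear from a row?** Only when no other postbaseline ECG meets that threshold. One scheduled ECG, at EOT or ET, falls after the Post-Withdrawal Visit. For example, suppose a patient meets the discontinuation criterion in Protocol 5.2.5 on a mean QTcF above 500 ms from three ECGs at an unscheduled visit. A mean above 500 ms implies at least one reading above it. Under the literal rule, the patient is missing from the >500 ms row if the ET ECG and every other postbaseline ECG are at or below 500 ms.

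**4. How much exposure is involved?** Inputs: 143 patients randomized to Part B (SAP 2.3); 12 weeks (84 days) of open-label treatment (SAP 2.1); EOT window of ±3 days (Part B schedule). The formula is patients × days / 365.25, assuming that all 143 complete.

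- 84 days: 143 × 84 / 365.25 = 32.9 patient-years
- 81 days: 143 × 81 / 365.25 = 31.7 patient-years
- 87 days: 143 × 87 / 365.25 = 34.1 patient-years

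Early terminations would reduce these figures.

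**5. What is one lost patient worth?** 1/143 = 0.7 percentage points of the Part B patients. In the combined table, if the safety population is near the planned enrolment of 330 (an assumption; the actual number is not given), it is 1/330 = 0.3 points. The documents do not give the number of unscheduled visits, ECGs or C-SSRS forms, so the expected number of lost patients cannot be computed.

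**The case against.** The strongest reply is that the sentence is about visits only. It sits in a section on study days and visit windows, under a paragraph that opens with by-visit analyses, and open-label Part B has a single scheduled visit. On that view it merely tells the programmer to assign ET data to EOT and to leave unscheduled data unassigned. This is probably what was meant. But the SAP says it prevails over the protocol, and SAP 9 does not list the exclusion or limit it, so nothing in the text corrects the broader wording.

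A second reply is that affected patients stay visible. Protocol 5.2.5 requires an ET visit when the QTcF criterion is met, ET data are kept, and Protocol 7.1.1 makes an abnormal assessment that leads to discontinuation an adverse event. This stands and limits the harm. It does not put the triggering reading into the outlier row.

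Three stronger readings are tempting, and the documents do not support them.

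- *Adverse events would be lost.* A reader might infer this from the words alone. The time-period block and SAP 7.1.3 give adverse events their own rule through the open-label EOT visit.
- *Part A unscheduled ECGs are stated to enter the any-time table while Part B ones are barred.* The Part A rule is expressly for by-visit analyses. The SAP does not say how Part A unscheduled readings are handled in SAP 7.1.7.
- *The SAP's own Part B QTcF measure is damaged.* SAP 2.2.1 confines that measure to the Randomized Withdrawal Period, which the sentence does not touch.

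The C-SSRS part can be put no higher than a possibility. Unscheduled assessments are done if indicated (Protocol 6.7). The form text is redacted, so whether the EOT form would recapture an earlier response cannot be checked.

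**Conclusion.** The point holds as a fault of wording with a real consequence if followed literally: ECGs from open-label unscheduled visits would be left out of the combined postbaseline outlier counts, and no other planned table makes good the loss. The same could happen to C-SSRS responses. For adverse events there is only an inconsistency to tidy.

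The effect runs one way, towards lower counts, and is probably small. It arises in at most about 33 patient-years, assuming all 143 patients complete 12 open-label weeks. It requires literal programming, an outlier at an unscheduled visit, and no other postbaseline ECG that qualifies. Each patient lost lowers a row by one. The comparison of SD-809 with placebo in the Randomized Withdrawal Period is not affected. Severity: minor.

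**What to change.** Replace the second sentence of the Part B Visits paragraph in SAP 4.5 with:

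> Data collected at unscheduled visits during Part B open-label treatment will not be used in by-visit summaries. All postbaseline readings, including those from unscheduled visits in Part A and Part B, will be included in the any-time postbaseline safety summaries (ECG outlier counts; C-SSRS any-time and shift tables), and adverse events will be analysed by time period as defined below.

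This keeps the term postbaseline from SAP 7.1.7 rather than narrowing it to on-treatment readings, and it settles the handling of both parts.

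The cost is this change to the SAP text and a small filter change in the ECG outlier and C-SSRS any-time programs. No new table or data collection is needed. By-visit summaries stay as planned. Outlier counts may become slightly less favourable.

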**Part A and B Combined:**

Some analyses, such as the analyses of adverse events, will be performed by time period. For these analyses, the following definitions will be used:

- Titration Period - from the first dose of treatment until 7 days after the week 6 visit. If a patient discontinues treatment before 7 days after the week 6 visit, then the Titration Period is until the last dose of treatment.
- Maintenance Period - from 8 days after the week 6 visit until the day of the week 158 visit for patients only in Part A and until the day of the open-label treatment EOT visit for patients in both Parts A and B. If a patient enters the Maintenance Period but discontinues treatment early, the Maintenance Period is until the last dose of treatment.

- Overall Treatment Period - includes the Titration and the Maintenance Periods, if applicable.
- Follow-up Period - from the end of the Overall Treatment Period through the end of the study.

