### **Part B:**

Part B will consist of a double-blind; Randomized Withdrawal Period; treatment with SD-809; and post-treatment safety follow-up. The Randomized Withdrawal Period will be 1 week (+3 days maximum) in duration and will consist of 2 visits, the Pre-Withdrawal Visit and the Post-Withdrawal Visit. After the Randomized Withdrawal Period, the patients will resume treatment with SD-809 on the prior established dose for an additional 12 weeks until end of treatment (EOT). A follow-up telephone call will occur 4 weeks after EOT.

At the beginning of the Randomized Withdrawal Period, patients will be randomized in a blinded fashion to either SD-809 (current dose) or placebo in a 1:1 ratio stratified by concomitant DRA usage. Up to 194 patients (active patients as of the approval date of Amendment 06) will be randomized (SD-809 or placebo). Patients will be required to sign a written informed consent.

Patients will need to be on a stable dose of SD-809 and any concomitant DRA for a minimum of 4 weeks before starting the Randomized Withdrawal Period.

Patients will be scheduled to return 1 week (+3 days maximum) after the Pre-Withdrawal Visit of the Randomized Withdrawal Period for efficacy and safety assessments.

At the end of this period, patients will continue treatment with SD-809 at the previous dose administered before the Randomized Withdrawal Period (last dose in Part A). Treatment with SD-809 will continue for 12 weeks until the EOT visit.

Video ratings of the AIMS will occur at the Pre-Withdrawal Visit, the Post-Withdrawal Visit, and the EOT/early termination (ET) visit.

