### **2.3. Sample Size and Power Considerations**

Because this is an open-label study, the sample size is not based on statistical considerations.

It is estimated that approximately 91 patients per arm in the Randomized Withdrawal Period will enable a power of at least 90% to detect a beneficial effect of 1.4 points or more in the change from pre-withdrawal to post-withdrawal in centrally read AIMS when the SD-809 arm is compared to placebo, assuming a standard deviation of 2.9 and a 2-sided type I error rate of 5%.

At the time of finalizing this SAP, all patients have started Part B, or completed part A, or have withdrawn from Part A. 143 patients were randomized to Part B, resulting in a power of approximately 80%.

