#### **7.1.2. Study Drug Administration**

Duration of treatment (days treated) is the number of days on treatment based on the first and last day of treatment with the study drug (last day of study drug – first day of study drug + 1). Weeks on treatment using the categories  $\geq 2$  weeks,  $\geq 4$  weeks,  $\geq 6$  weeks,  $\geq 15$  weeks,  $\geq 28$  weeks,  $\geq 41$  weeks,  $\geq 54$  weeks,  $\geq 67$  weeks,  $\geq 80$  weeks,  $\geq 93$  weeks,  $\geq 106$  weeks,  $\geq 119$  weeks,  $\geq 132$  weeks,  $\geq 145$  weeks,  $\geq 158$  weeks and  $\geq 171$  weeks will be summarized using descriptive statistics. Duration of treatment (days) will also be summarized as continuous data using descriptive statistics.

Total daily dose (mg) will be summarized as continuous data at each Part A visit using descriptive statistics. In addition, total daily dose (mg) will be summarized by individual dose and dose categories ( $< 24$  mg,  $\geq 24$  to  $\leq 36$  mg,  $> 36$  to  $\leq 48$  mg, and  $> 48$  mg) as categorical data at each Part A visit using descriptive statistics.

Percent treatment compliance is calculated as  $100 \times (\text{number of tablets used} / \text{number of tablets expected to be used})$ . The number of tablets used is the number of tablets dispensed minus the number of tablets returned. If a patient does not return the pill bottle, it will be assumed that the patient took no study medication from that bottle for the purposes of calculating compliance. The number of tablets expected to be used is based on the number of morning and evening dosing times during the treatment period (1 tablet is used for each dosing time point). A patient will be deemed compliant over the treatment period if the patient has taken 80% to 105% of the expected tablets of study drug.

Percent treatment compliance will be summarized as continuous data using descriptive statistics. In addition, percent treatment compliance will be summarized as categorical data using descriptive statistics for the following categories:  $< 80\%$ , 80% to 105%,  $> 105\%$ .

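### The combined safety periods and patient-years count the placebo withdrawal week as treatment, so off-drug days and events are pooled with SD-809 experience, with a probably small effect of unknown direction

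*SAP*

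**What the plan says.** SAP 4.5 (Part A and B Combined) defines the periods used for adverse events. Maintenance starts 8 days after the Week 6 visit and runs "until the day of the open-label treatment EOT visit for patients in both Parts A and B". The next definition reads "Overall Treatment Period - includes the Titration and the Maintenance Periods, if applicable". Events after that span go to a Follow-up Period, which SAP 7.1.3 summarises separately.

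SAP 7.1.1 sets the layout of the main safety tables: "Summaries will be presented by parent study treatment group and overall", and "Summaries will be presented for Parts A and B combined unless otherwise noted". The columns are therefore the parent-study arms, not the Part B arms.

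SAP 7.1.2 defines duration of treatment as "the number of days on treatment based on the first and last day of treatment with the study drug", that is, last minus first plus 1. In SAP 7.1.3 the event rate divides by patient-years in both Parts, the EAIR uses the same exposure up to the first event, and in the time-to-first-event curves "patients who do not experience the event will be censored at the end of treatment in Parts A and B combined".

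In the SAP's description of Part B, "patients will be randomized in a blinded fashion to either SD-809 (current dose) or placebo in a 1:1 ratio", with the second visit 7 to 10 days later. SAP 2.3 reports that "143 patients were randomized to Part B". SAP 7.2.3 plans one adverse-event summary for the withdrawal period: all events by system organ class and preferred term, split by randomised arm under SAP 7.2.1.

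**The concern.** The first study objective is the safety of long-term SD-809 therapy, and the combined Part A and B tables are the main answer to it. During the withdrawal week about half of the Part B patients were not taking SD-809, but their days count as treatment time and their events as treatment-period events. The tables are not split by Part B arm, so a reader cannot separate the two.

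The SAP does make this separation elsewhere. Once treatment ends, new events leave the treatment period and are shown on their own. A planned off-drug interval with known dates is handled the other way.

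The Part B table does not repair this. SAP 2.2.1 names serious, drug-related and withdrawal-causing events as Part B endpoints, and Protocol 8.4 adds severe events. SAP 7.2.3 tabulates none of these separately and has no SMQ breakdown. The summary tables that classify events on these attributes are the combined ones.

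**Working it through.** The plan gives no figure for exposure or adverse events in the withdrawal week, so there is nothing of its own to reproduce here. Its Part B power figures do not enter this point.

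**1. Do the definitions exclude the week?**
- Period: Maintenance has no gap between its start and the open-label EOT visit (SAP 4.5).
- Duration: last minus first plus 1 spans any interval between. Reading 'study drug' as SD-809 alone would not change this, and Protocol 5.1 (Study Drug) includes placebo as 5.1.2.
- Event rate, EAIR and censoring: all use Parts A and B combined (SAP 7.1.3).

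No rule removes or marks the placebo days.

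**2. Placebo time.** Inputs: 143 randomised (SAP 2.3), 1:1 allocation (SAP 2.4), 7 to 10 days (SAP 2.1). Patients on placebo: 143 / 2 = 71.5, so 71 or 72.
- 7 days: 71.5 × 7 / 365.25 = 1.37 patient-years.
- 10 days: 71.5 × 10 / 365.25 = 1.96 patient-years.

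**3. Share of all person-time.** Total exposure is not given. Assume the planned 330 patients (Protocol synopsis, Sample Size) with a mean of 1 to 2.5 years each, giving 330 to 825 patient-years.
- Smallest: 1.37 / 825 = 0.17%.
- Largest: 1.96 / 330 = 0.59%.

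**4. Share of the EAIR band from Week 158 on.** Assume that every Part B patient entered at Week 158, which puts the whole withdrawal week in this band. Each then contributes 7 to 10 days plus 12 weeks (84 days). Before any truncation at a first event, the placebo share is:
- 0.5 × 7 / (7 + 84) = 3.8%.
- 0.5 × 10 / (10 + 84) = 5.3%.

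Patients who entered earlier had their placebo week in an earlier band, so the real share is probably lower.

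**5. Effect of one event.** Each event with onset in the placebo interval adds 100 / 825 = 0.12 to 100 / 330 = 0.30 per 100 patient-years to the combined event rate.

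**6. Direction.** Let E events occur in T patient-years overall, with e of them in p placebo patient-years. Excluding the interval changes E / T to (E − e) / (T − p). The rate falls only if e / p exceeds E / T, and otherwise it rises or stays the same. If e = 0, inclusion understates the rate by p / T, which is 0.17% to 0.59% on the exposure in step 3. If e is 1 or more in a sparse category, the rate may be overstated, by an amount that depends on E. The documents give neither e nor E.

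**The case against.** The strongest reply has five parts.

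**Nothing is hidden or mislabelled.** The period names do not mention SD-809, the tables are declared to combine both Parts, and withdrawal-week events appear by randomised arm in SAP 7.2.3. SAP 7.2.7 summarises the motor, akathisia, mood, suicidality and sleepiness scales by randomised arm, and SAP 7.1.3 plans listings of serious and discontinuation events. This stands against any charge of concealment. It does not correct the combined rates, because every other day in those periods is SD-809 treatment.

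**Inclusion is conservative.** Early placebo-week events may stem from the last SD-809 doses or be withdrawal effects, and arguably belong to the drug's safety profile. This is a good reason not to delete them. It does not justify pooling them unmarked, given the separate Follow-up Period.

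**Other gaps are left in.** Protocol 5.2.5 allows suspension of study drug, and those days also stay inside last minus first plus 1. That is correct, so the inconsistency lies only with the treatment of off-drug time after the end of treatment. The placebo interval differs in being planned, randomised and exactly dated.

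**The SMQ route is weak.** A reader might infer that returning dyskinesia on placebo will be scored as SD-809 akathisia or parkinsonism. The documents do not show this. Appendix A lists neither dyskinesia nor tardive dyskinesia in those groups, and Protocol 7.2 asks sites for a unifying diagnosis and for wording that shows worsening of a past condition. 'Movement disorder' and 'Motor dysfunction' are in both lists, and 'Hyperkinesia' and 'Restlessness' in the akathisia list only, so misclassification is possible but depends on coding.

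**Any large percentage would be invented.** Four placebo-week events added to ten others would look like a 40% overstatement, but both counts are assumed. The sum ignores events that would have occurred anyway. It also ignores that incidence tables count a patient once per term, and that EAIR and Kaplan-Meier use first events only. This stands in full.

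**Conclusion.** The definitions pool 7 to 10 placebo days for 71 or 72 patients, and any events starting in them, with SD-809 experience in the combined safety outputs. That follows directly from the text and does not depend on any assumption about event rates.

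The effect on all-AE rates is probably negligible, given the 0.17% to 0.59% share of person-time on the assumed exposure. It could matter for sparse SAE or SMQ categories and for the last EAIR band, where the placebo share could reach 3.8% to 5.3% under the Week 158 assumption. Its size and direction cannot be determined from the documents. A reader might conclude that the SAP blames the drug for events caused by stopping it. That needs an event rate for the placebo week, and a cause for those events, that the documents do not give.

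This is worth correcting because the definition is wrong for its purpose and cheap to mend, not because a material bias has been shown.

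**What to change.** In SAP 4.5, define a placebo-interval flag for patients randomised to placebo, from the first blinded placebo dose to the day before SD-809 is resumed. Use actual dates, so that late returns are covered.

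In SAP 7.1.2 and 7.1.3, subtract the flagged days from SD-809 patient-years. Present the combined event-rate, EAIR, SAE, treatment-related, SMQ and Kaplan-Meier results with flagged events excluded from the on-SD-809 counts and shown in a placebo-week row or column of their own, so that no event drops out of the safety report. Keep the all-inclusive version beside it, with a footnote saying that its periods include the placebo week.

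The cost is a short addition to the SAP, one date flag in the adverse-event and exposure datasets (set after unblinding), and second versions of some tables. The change concerns analysis definitions only and touches no dosing or clinical-management rule.
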